10.3 Data Analyses

Objective response rate, and disease control rate with corresponding 2-sided 95% CIs will be estimated using the Clopper-Pearson method. Kaplan-Meier methods will be used to estimate medians and 95% CIs for duration of response, overall survival, and progression-free survival. Survival outcomes will be calculated from Day 1 of Cycle 1. Descriptive statistics will be used to analyze AEs described according to the NCI CTCAE v5.0. Clinically significant laboratory abnormalities will be described as well. Serious adverse events will be summarized, including a causality assessment. The number of treatment cycles and doses administered will be summarized using descriptive statistics.

Associations between molecular features and tumor response will be analyzed using the Fisher-exact test with Benjamini-Hochberg multiple-testing correction. Cox regression models will be used to assess for associations between overall survival or progression-free survival and exploratory and correlative measures.

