Diagnosis and Main Inclusion Criteria	
 1. Patients must have a histologically confirmed diagnosis of hepatocellular carcinoma; 2. No history of prior systemic therapy for HCC; 3. Patients with advanced HCC not eligible for curative and/or locoregional therapies; 4. Age ≥ 18 years; 5. Child-Pugh Score A
Study Product(s), Dose, Route, Regimen	Axitinib 5 mg PO BID Avelumab 10 mg/kg IV every 2 weeks (maximal dose of 2000 mg; 2 doses in a 4-week cycle) Baviximab 3 mg/kg IV every 1 week (4 doses in a 4-week cycle)
Duration of administration	Study treatment will continue until disease progression, unacceptable toxicity, death, or discontinuation from the study treatment for any other reason.

Statistical Methodology	Safety and tolerability assessment will be performed for the first 6 evaluable patients in the safety lead-in. The primary endpoint of the trial will be objective response rate (ORR). A minimax two-stage method will be used to analyze ORR after the first 14 patients are accrued. 15 additional patients will be enrolled if 2 or more of the first 14 patients have either a complete or partial response.
-------------------------	---

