McNamara et al. conducted a single-arm phase II trial of axitinib in patients with advanced HCC refractory to prior antiangiogenic treatments and had Child-Pugh Class A/B7 liver disease.¹⁶ Axitinib was started at 5 mg twice daily orally, and titrated from 2 to 10 mg twice daily as tolerated. Of 26 patients evaluable for response, there were 3 partial responses per RECIST 1.1, and 6 partial responses and 1 complete response by modified RECIST. However, the median progression-free survival and overall survival of 3.6 and 7.1 months was disappointing. The most frequent axitinib-related grade 3/4 AEs were hypertension, thrombocytopenia, and diarrhea.

Chan et al. conducted a single-arm phase II trial in patients with inoperable HCC who underwent transarterial chemoembolization followed by maintenance axitinib 5 mg twice daily. The primary endpoint was the 2-year overall survival rate. In the intention-to-treat population (50 patients), the 2-year survival rate was 43.7%, which failed to meet the prespecified hypothesis of a 2-year survival rate of 50%. Grade 3 or greater axitinib-related complications included hand-foot skin reaction (14%) and hypertension (24%).

Clinical experience of axitinib combined with immunotherapies in advanced HCC is limited to a single phase 1B trial (VEGF Liver 100) in which interim results were reported on 22 patients treated with avelumab 10 mg/kg every two weeks plus axitinib 5 mg orally twice daily.¹⁷ The most common grade 3 treatment-related AEs were hypertension (50.0%) and hand-foot syndrome (22.7%) and no grade 4/5 toxicities were observed. Objective response rates were 13.6% (95% CI, 2.9%-34.9%) and 31.8% (95% CI, 13.9%-54.9%) by RECIST and mRECIST, respectively. OS data were immature at data cutoff. These preliminary findings demonstrate that axitinib combined with avelumab was safe, consistent with the known safety profiles of avelumab and axitinib when administered as monotherapies.

Complete information for axitinib may be found in the axitinib Investigator's Brochure.

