10.2 Sample Size and Accrual

We will use a minimax two-stage design method to compare the objective response rate of 34% (alternative hypothesis) for the treatment cohort versus 14% (null hypothesis) for the historical control. The basis of the null response rate is based on the previously reported objective response rate of 14% for axitinib plus avelumab in advanced HCC. This design

requires a sample size of 29 evaluable patients to yield a type I error rate of 0.10 and power of 0.9 when the true response rate is 34%. In the first stage 14 evaluable patients will be accrued. If there are 2 or more responses, then 15 additional evaluable patients will be accrued. Thus, the total enrollment for this study will be up to 29 evaluable patients. The null hypothesis will be rejected if 7 or more responses are observed in 29 patients. Objective response rate is defined as number of responders (either complete or partial response as the best objective response) of eligible patients. Patients who attain a complete response, partial response, or stable disease but do not have two imaging assessments to confirm response will be replaced.

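### Does the planned 95% interval for ORR conflict with the 0.10-level two-stage rule when 7 or 8 of 29 patients respond?

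*Combined protocol and SAP*

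**What the plan says.** Section 10.2 sets the hypotheses as "objective response rate of 34% (alternative hypothesis) for the treatment cohort versus 14% (null hypothesis) for the historical control". The design "requires a sample size of 29 evaluable patients to yield a type I error rate of 0.10 and power of 0.9" when the true rate is 34%. Fourteen evaluable patients enter first, and 15 more follow if at least 2 respond; section 7.6 gives the same futility rule. The final criterion is a count: "The null hypothesis will be rejected if 7 or more responses are observed in 29 patients".

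Section 10.3 turns to estimation: "Objective response rate, and disease control rate with corresponding 2-sided 95% CIs will be estimated using the Clopper-Pearson method". It contains no test of ORR against 14%. It gives no two-stage p-value, no interval at another level, and no remark on how the 95% interval relates to the rule in 10.2.

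The Study Summary, under Statistical Methodology, says: "A minimax two-stage method will be used to analyze ORR after the first 14 patients are accrued". The sentence after it gives the condition for enrolling the remaining 15 patients.

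**The concern.** A two-sided 95% interval leaves 2.5% in each tail. The rule in 10.2 rejects only for high counts, so its 0.10 all lies in one tail. The interval is therefore stricter than the test, and some results that reject 14% come with an interval that includes it. A reader who checks the published interval against 14% would see a positive trial that seems to contradict itself. In effect that reader would be asking for 9 responses rather than 7.

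The planned interval also treats the 29 patients as a fixed sample, although the trial can stop after 14. That raises a second question, whether its coverage holds under the design. If the interval decided success, or if its coverage were poor, the primary result would be at stake.

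**Working it through.** **Inputs.** From section 10.2: p0 = 0.14, p1 = 0.34, n1 = 14, continue if X1 ≥ 2, n2 = 15, reject if the total S ≥ 7 of 29. From section 10.3: two-sided 95% Clopper-Pearson. The protocol does not state whether the 0.10 is one-sided. I read it as one-sided because only high counts reject, and the calculation below bears that out. All figures assume exactly 29 analysed patients if the trial continues.

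**1. The plan's own figures.** For a threshold s,

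P(continue and S ≥ s | p) = Σ over x = 2..14 of Bin(x; 14, p) × P(Bin(15, p) ≥ s − x).

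- Early stop at 14%: 0.86^14 + 14 × 0.14 × 0.86^13 = 0.121 + 0.276 = 0.397.
- Type I error, s = 7 at 14%: 0.0973.
- Power, s = 7 at 34%: 0.9002.

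Both agree with the stated 0.10 and 0.9. A search over two-stage designs meeting those limits finds 29 as the smallest maximum size. Among the designs with 29 patients, this one has the smallest expected size under the null: 14 + 15 × (1 − 0.397) = 23.05.

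**2. Planned interval beside the decision.** The Clopper-Pearson limits are the 0.025 quantile of Beta(s, 30 − s) and the 0.975 quantile of Beta(s + 1, 29 − s). The two-stage p-value is the sum above at p = 0.14.

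| Responses | Planned 95% interval | Contains 14%? | Two-stage p-value | Decision under 10.2 |
|---|---|---|---|---|
| 6/29 | 8.0% to 39.7% | yes | 0.198 | do not reject |
| 7/29 | 10.3% to 43.5% | yes | 0.097 | reject |
| 8/29 | 12.7% to 47.2% | yes | 0.041 | reject |
| 9/29 | 15.3% to 50.8% | no | 0.0145 | reject |

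The mismatch is real at 7 and 8. Rounding of the null does not cause it: the unrounded 13.6% in section 1.2.3 also lies inside both intervals.

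**3. How often it would arise.** P(S = 7 or 8):

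- At 34%: 0.0835 + 0.1216 = 0.205, which is 0.205/0.900 = 23% of rejections.
- At 24%: 0.308, which is 0.308/0.551 = 56% of rejections.
- At 14%: 0.0567 + 0.0261 = 0.083, which is 0.0828/0.0973 = 85% of rejections. Here 14% is the true rate, so an interval containing it is correct.

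**4. Level or stages?** The lower limit that respects the two stages solves P(continue and S ≥ s | p) = tail level. At 7/29:

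| Tail | Ignoring stages | Using stages |
|---|---|---|
| 0.025 | 10.30% | 10.38% |
| 0.10 | 13.97% | 14.09% |

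Moving the tail from 0.025 to 0.10 raises the limit by 13.97 − 10.30 = 3.67 points. Accounting for the stages moves it by 0.08 or 0.12 point. So the gap is almost entirely the confidence level.

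**5. Is the planned interval trustworthy?** I took the coverage over all outcomes of the design, using 14 as the denominator when the trial stops early and 29 otherwise. On a 0.1-point grid of true rates from 5% to 60%, the minimum is 94.8%, at 23.5%. That is about nominal, so the planned interval needs no adjustment for the stages.

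**The case for a change.** The best case for a change is about how the result will be read. This is a single-arm trial judged against a fixed historical rate, and its report will show an estimate and an interval. A success at 7 or 8 responses is not rare, and its interval will seem to dispute the claim. Explaining this afterwards can look like special pleading, whereas a sentence written beforehand does not. Nor is there an easy substitute: at 7/29 the lower limit of an ordinary 90% interval is 11.9% and that of an 80% interval is 13.97%, both still below 14%. Full agreement needs the 0.10 level and the two-stage calculation together (14.09% at 7/29, 16.84% at 8/29).

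All of that arithmetic stands, but it does not show a defect. Reading the interval as a test amounts to a 9-or-more rule, with power 69.5% at 34%. That rule appears nowhere in the protocol, so the figure is not an operating characteristic of this trial. The Study Summary's reference to a two-stage method concerns the look after 14 patients and promises no two-stage interval or p-value at the end. A second interval would bring its own explaining: readers at 7/29 would see lower limits of 10.3% and 14.1%, and the matched limit clears the null by only 0.09 point.

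**Conclusion.** No change follows. Section 10.2 gives one explicit and correctly sized criterion for success, and section 10.3 uses the interval only to estimate. A conventional 95% interval beside a one-sided 0.10 phase II rule is a fair trade-off: the rule is set for a go/no-go decision in few patients, and the interval shows how imprecise the estimate is.

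The two disagree only at 7 and 8 responses, with probability 20.5% if the true ORR is 34%. At those counts the decision is still the one the plan prescribes. No error rate, decision or patient is affected. An analyst writing the report would naturally call the interval descriptive, cite the count rule, and could quote the two-stage p-value (0.097 at 7, 0.041 at 8) without any amendment.

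This rests on reading the 0.10 as one-sided, which the exact reproduction supports, and on 29 analysed patients. With a different denominator the listed limits and p-values would shift, but the distinction between a decision rule and an estimation interval would not.

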2.4 Endpoints

Primary endpoint:

Objective response rate (ORR) based on Investigator assessment per RECIST v.1.1.

Secondary endpoint:

Progression-free survival (PFS), overall survival (OS), and duration of response (DR) based on Investigator assessment, per RECIST v.1.1.

Adverse events (AEs) and laboratory abnormalities as graded by National Cancer Institute (NCI) Common Terminology Criteria for Adverse Events (CTCAE) v5.0.

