6.2 Safety/Tolerability

Analyses will be performed for all subjects having received at least one dose of study therapy. The study will use the CTCAE version 5.0 for reporting of adverse events. https://ctep.cancer.gov/protocolDevelopment/electronic_applications/ctc.htm

A safety lead-in phase composed of the first six patients evaluable for dose-limiting toxicities as defined in Section 4.2 will be performed to ensure the safety and tolerability of this triplet regimen.

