7.4.1 Definitions

An adverse event is defined as any untoward or unfavorable medical occurrence in a human research study participant, including any abnormal sign (for example, abnormal physical exam, imaging finding or clinically significant laboratory finding), symptom, clinical event, or disease, temporally associated with the subject's participation in the research, whether or not it is considered related to the subject's participation in the research.

Adverse events encompass clinical, physical, and psychological harms. Adverse events occur most commonly in the context of biomedical research, although on occasion, they can occur in the context of social and behavioral research. Adverse events may be expected or unexpected.

Severity

Adverse events will be graded by a numerical score according to the defined NCI Common Terminology Criteria for Adverse Events (NCI CTCAE) Version 5.0. Adverse events not specifically defined in the NCI CTCAE will be scored on the Adverse Event log according to the general guidelines provided by the NCI CTCAE and as outlined below.

- Grade 1: Mild
- Grade 2: Moderate
- Grade 3: Severe or medically significant but not immediately life threatening
- Grade 4: Life threatening consequences
- Grade 5: Death related to the adverse event

Serious Adverse Events

OHRP and UTSW HRPP define serious adverse events as those events, occurring at any dose, which meets any of the following criteria:

- results in death;
- is life-threatening (places the subject at immediate risk of death from the event as it occurred);
- results in inpatient hospitalization^{1,2} or prolongation of existing hospitalization;
- results in a persistent or significant disability/incapacity;

- results in a congenital anomaly/birth defect; or
- based upon appropriate medical judgment, may jeopardize the subject's health, and may require medical or surgical intervention to prevent one of the other outcomes listed in this definition.

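### The secondary endpoint covers all CTCAE-graded laboratory abnormalities, but the only laboratory-specific analysis covers an undefined clinically significant subset, so full reporting of the endpoint is not assured

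*Combined protocol and SAP*

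**What the plan says.** Section 2.4 (Endpoints) sets the secondary safety endpoint as "Adverse events (AEs) and laboratory abnormalities as graded by National Cancer Institute (NCI) Common Terminology Criteria for Adverse Events (CTCAE) v5.0". Laboratory abnormalities stand beside adverse events as a component of their own, and the grading scale is the only qualifier. Section 2.2.2 makes the overall safety profile of the triplet a secondary objective.

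Section 10.3 (Data Analyses) has two relevant sentences. The first covers adverse events: "Descriptive statistics will be used to analyze AEs described according to the NCI CTCAE v5.0". The second covers laboratory results: "Clinically significant laboratory abnormalities will be described as well". The protocol gives no grade cut-off or other criterion for clinical significance and does not say who determines it. No section plans a table of laboratory results by CTCAE grade or of shifts from baseline.

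Section 7.4.1 defines an adverse event broadly. Its parenthetical examples of an abnormal sign are "abnormal physical exam, imaging finding or clinically significant laboratory finding".

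Section 6.2 sets the safety population: "Analyses will be performed for all subjects having received at least one dose of study therapy".

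**The concern.** An endpoint and its analysis should cover the same set of events. Here the endpoint is every graded laboratory abnormality, while the analysis written for it is a subset whose boundary is not drawn. Two analysts with the same laboratory data could produce different tables, and neither would have departed from the plan.

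The laboratory part of the safety profile is at stake. Section 3.1.8 admits patients with AST and ALT up to 5 times the upper limit of normal, so some will enter with abnormal hepatic tests. An on-treatment grade is hard to interpret in such a patient without the baseline grade beside it. The trial has a single arm, so no concurrent comparator would show whether laboratory abnormalities had been incompletely reported.

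**Working it through.** The point rests on comparing texts. The plan states no expected laboratory abnormality rate, so there is no figure to reproduce.

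1. **What the endpoint requires.** Section 2.4: laboratory abnormalities, graded by CTCAE v5.0. Call the number of patients with such an abnormality, for a given test and grade, G.

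2. **What the laboratory sentence delivers.** Section 10.3: abnormalities that are clinically significant, with no definition. Call the corresponding number of patients S. These patients are a subset of those counted in G, so S ≤ G. Equality holds only if every patient in G has an abnormality that counts as clinically significant.

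3. **What the adverse event sentence adds.** Section 10.3 also summarises adverse events by CTCAE grade. Let A be the number of patients in G whose abnormality was recorded as an adverse event. The two summaries together reach the patients counted in S or A or both, and this number again cannot exceed G.

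4. **Whether A closes the gap.** It would if every graded abnormality had to be recorded as an adverse event. Section 7.4.1 does not require that. Its laboratory example carries the same qualifier as section 10.3. An example does not exclude other findings, so a graded abnormality outside it may still be recorded, but nothing obliges it to be.

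5. **Which abnormalities are exposed.** Table 3 in section 4.2.3 is a table of drug-related adverse events. It lists AST, ALT or bilirubin elevation by grade, and it has rows for hematologic abnormalities and for other laboratory abnormalities. Events managed under it are adverse events by the protocol's own classification and belong in the section 10.3 summary. The exposed remainder is therefore mainly asymptomatic or lower-grade change that nobody records as an adverse event.

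6. **Size.** The shortfall is G minus the number reached in step 3. The documents give neither G nor the share that would be clinically significant or recorded as adverse events. The direction is fixed, since the shortfall cannot be negative, but its size cannot be estimated and may be zero.

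7. **Denominator.** Section 10.2 states: "Thus, the total enrollment for this study will be up to 29 evaluable patients". That figure counts patients evaluable for response, and the same section provides for replacing some patients. Section 6.2 uses everyone who received a dose, which may be more than 29. A laboratory table should use the section 6.2 population.

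8. **Whether the data will exist.** Sections 5.2 and 5.3 schedule a complete blood count, metabolic panel, coagulation tests, lipase, thyroid function and urinalysis at screening and on Day 1 of each cycle, with the metabolic panel again on Day 15. Grade and shift tables need no extra sampling.

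**The case against.** The strongest reply is that section 10.3 is additive. The laboratory sentence ends by saying that these abnormalities are described as well, after a CTCAE-based adverse event summary that already contains laboratory findings recorded as adverse events. The definition in section 7.4.1 takes in any untoward occurrence and any abnormal sign, and its laboratory phrase is only an example. Section 1.2.9 reports a bavituximab plus pembrolizumab study at the same centre in which AST increase (5 of 36, 13.9%) and ALT increase (4 of 36, 11.1%) appear as treatment-related adverse events with none at Grade 3 or 4. Low-grade laboratory changes evidently can reach an adverse event table. In addition, section 5.3 requires laboratory review before each cycle, and section 11.4 has the data safety monitoring committee review adverse events quarterly. Patient oversight therefore does not depend on section 10.3.

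Much of this stands, and it rules out three stronger readings.

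- A reader might infer that an investigator's judgment decides which graded abnormalities are reported. The documents do not say who decides or how; a grade-based criterion would fit the wording equally well.
- A reader might infer that the hepatic changes for which Table 3 holds or reduces axitinib would drop out of the safety results. Table 3 classes them as graded adverse events, which section 10.3 summarises.
- A reader might infer that the reported rates are biased downward. A rate labelled as that of clinically significant abnormalities is a different quantity from the graded endpoint. It understates the endpoint only if it is presented as the endpoint and some graded abnormalities have been left out, and the documents establish neither.

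The reply does not supply the missing analysis. No sentence commits the trial to reporting graded laboratory abnormalities as section 2.4 defines them, and the term that limits the laboratory summary has no definition.

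**Conclusion.** The mismatch is in the text. The endpoint in section 2.4 is unrestricted; the laboratory-specific analysis in section 10.3 is restricted by an undefined term; and the adverse event summary covers part of the difference without assuring all of it. Following section 10.3 as written may understate the laboratory endpoint, mainly for asymptomatic or lower-grade abnormalities, by an amount the documents do not allow to be estimated.

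This rests on two assumptions: that section 2.4 means what it says in listing laboratory abnormalities as their own component, and that no other planning document, not among those reviewed, supplies the laboratory tables.

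Severity is minor. The endpoint is secondary and descriptive. The primary response analysis, the two-stage rule and the safety lead-in decision do not depend on this sentence.

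**What to change.** In section 10.3, replace the laboratory sentence with a commitment along these lines: for each scheduled laboratory test that CTCAE v5.0 grades (sections 5.2 and 5.3), worst post-baseline grade and shift from baseline grade will be tabulated from the laboratory values, regardless of clinical significance, for all patients who received at least one dose. State which pre-treatment value is baseline; the last one before the first dose would serve.

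Keep clinically significant abnormalities as an additional listing, labelled as such, with a one-line definition of the term.

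The cost is a few programmed tables. No visit, sample or patient is added. The safety display may look less favourable, because graded changes that were not recorded as adverse events would now be shown.

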1.5 Correlative Studies

Molecular profiling including exome and transcriptome sequencing of baseline or multiplex immunohistochemistry of archived tissue specimens will allow us to identify predictive markers of treatment response. As this testing will be performed on tissue obtained as a component of routine care, there is no additional risk to the patient. Tissue sampling at the time of progression is encouraged but not required. Tissue at progression may undergo similar testing to identify markers or mechanisms of resistance.

Archival tissue will also be examined using the Xerna™ TME Panel which is a RNA-based gene expression assay to classify patients based on the biology of the tumor microenvironment (TME).

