9.0 CORRELATIVES/SPECIAL STUDIES

The goal of the planned laboratory correlative studies is to assess genetic mechanisms of immunotherapy resistance. Analyses will be performed on tissue specimens collected as a component of routine clinical practice, and thus no additional specimen collection solely for research purposes is required.

Archival or baseline tumor tissue will be genomically characterized by MI Profile (Caris Life Sciences). This will allow us to assess whether mutations, copy number alterations, and RNA signatures may be associated with different clinical outcomes.

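### Section 10.3 applies Benjamini-Hochberg to Fisher tests in at most 29 patients with no rule for alterations too rare to be significant; a margin-only filter would recover power at no cost in error control

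*Combined protocol and SAP*

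**What the plan says.** The plan for the molecular analysis is one sentence in section 10.3: "Associations between molecular features and tumor response will be analyzed using the Fisher-exact test with Benjamini-Hochberg multiple-testing correction". The FDR level, the family of features, their number and any minimum number of carriers are not stated.

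The features are described elsewhere. Section 1.5 plans "Molecular profiling including exome and transcriptome sequencing of baseline" or multiplex immunohistochemistry of archived tissue, plus an RNA-based classifier of the tumor microenvironment. Of the tumor profiling, section 9.0 says: "This will allow us to assess whether mutations, copy number alterations, and RNA signatures may be associated with different clinical outcomes". Looking for markers that predict response is an exploratory objective (2.3.2).

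The number of patients is fixed by the primary design. Section 10.2 says that "the total enrollment for this study will be up to 29 evaluable patients", with 34% response under the alternative and 14% under the null, and: "The null hypothesis will be rejected if 7 or more responses are observed in 29 patients".

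**The concern.** Fisher p-values are discrete. In a small sample, the number of altered patients and the number of responders together set a floor below which the p-value cannot fall. A feature with its floor above the FDR level can never be rejected, but plain Benjamini-Hochberg counts it in m, the number of tests. Every threshold q·i/m then becomes stricter for the features that could show an association. The procedure stays valid but is more conservative than it needs to be. What is at stake is part of the limited power that 29 patients offer for objective 2.3.2.

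**Working it through.** **Design figure.** Continuing with at least 2 responses in 14 and rejecting with at least 7 in 29, exact binomial sums give a type I error of 0.0973 at 14% and power of 0.9002 at 34%. Section 10.2 is reproduced, so N = 29 is a sound basis. Relevant responder counts are 7 (the rejection boundary) and about 10 (0.34 × 29 = 9.9).

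**Smallest attainable p-value.** With R responders of 29 and k carriers (k ≤ 3 here), the most extreme table has every carrier responding. Its probability is C(R,k)/C(29,k), and for these margins that is also the two-sided p-value.

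| Carriers k | R = 7 | R = 10 |
|---|---|---|
| 1 | 7/29 = 0.241 | 10/29 = 0.345 |
| 2 | 21/406 = 0.052 | 45/406 = 0.111 |
| 3 | 35/3654 = 0.0096 | 120/3654 = 0.033 |

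At 7–10 responders, 3 carriers are needed to reach 0.05. With 4 responders, 2 carriers suffice (6/406 = 0.015), so the cutoff must come from the observed margins and not from a fixed count.

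**How often a feature falls below 3 carriers.** P(X ≤ 2) for X ~ Binomial(29, prevalence) is 0.94 at 3% prevalence, 0.82 at 5%, 0.43 at 10%, 0.17 at 15%, 0.05 at 20% and 0.003 at 30%. It crosses one half at about 9%.

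**Effect on the threshold.** Suppose m = 100, q = 0.05 and 75 features are untestable. The first threshold is 0.05/100 = 0.0005 with all features and 0.05/25 = 0.002 without the untestable ones.

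**Power, by simulation.** All inputs are assumptions: 29 patients; one true marker in 30% of patients; rare features altered in 1–5% and the others in 5–40%; features with no carrier left out; overall response about 34%; FDR 5%; filter cutoff 0.05.

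| Share rare | Response, carriers vs others | Power, 100 features | Power, 600 features |
|---|---|---|---|
| 90% | 85% vs 12% | 0.62 → 0.79 | 0.37 → 0.58 |
| 85% | 85% vs 12% | 0.59 → 0.74 | 0.35 → 0.54 |
| 85% | 70% vs 19% | 0.16 → 0.28 | 0.04 → 0.11 |
| 85% | 60% vs 23% | 0.05 → 0.11 | 0.01 → 0.03 |

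With 80% rare, the gain for strong markers was 12–14 points; with half rare, 5–7. With 20 features, none rare, it was about 2.

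I repeated this with 1,000 runs per setting, 20 to 600 features, FDR 5% and 10%, and the cutoff equal to q. Gains were about 0–4 points with 10% of features rare, 0–9 with half rare and 3–22 with 90% rare. Within simulation error, these match the summary ranges of 0–4, 0–8 and 3–21. Realised FDR after filtering stayed below 0.02 at nominal 5% and below 0.04 at nominal 10%.

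**Why nothing is lost when the cutoff equals q.** Benjamini-Hochberg rejects only p-values at or below q·i/m, which is at most q. A feature whose floor exceeds q is therefore never rejected. Removing it lowers m to m′ and raises every threshold from q·i/m to q·i/m′, so all previous rejections remain. No simulated data set lost a rejection. The filter uses only the margins on which Fisher's test already conditions, so null p-values keep their validity, and the correction keeps its guarantee under its usual dependence conditions.

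**The case against.** The strongest reply is that section 10.3 does not say which features enter the correction. Leaving out alterations seen in one or two patients is compatible with its wording. A reader might infer that the correction covers every alteration detected and that most tests cannot reach 0.05. The documents support neither. The family is undefined, no prevalences are given, and most features being untestable would need most of them to have a prevalence below about 9%. RNA signatures, immunohistochemistry markers and microenvironment classes need not be rare. What stands is that no rule is written, so any cutoff would have to be chosen later, possibly with results in view.

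A second reply is that sample size is the main limit. That is largely right. For a moderate marker (60% vs 23%), power after filtering is about 0.12 or less with 100 or more features at FDR 5%. It can be higher in a smaller family dominated by rare features: 0.22 with 20 features, 90% of them rare. The large absolute gains belong to strong markers; 85% vs 12% is an odds ratio of about 42.

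A third reply concerns a filter fixed at 0.05, which is not free of loss if the FDR level is 10%. Two-carrier features with 7, 8 or 9 responders have floors of 0.052, 0.069 (28/406) and 0.089 (36/406), and could in principle be rejected. This is correct, and it is why the cutoff should equal q.

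Finally, unfiltered Benjamini-Hochberg is valid and misleads no one. This is an avoidable inefficiency and not an error.

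**Conclusion.** The point holds as a low-priority improvement. At N = 29 with 7–10 responders, alterations in 1 or 2 patients cannot reach p<0.05, and section 10.3 has no rule that keeps them out of the correction. If they are tested, the power cost is about 0–4 points when few features are rare, 0–8 when half are, and 3–21 when around 90% are (altered in 1–5% of patients).

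These ranges rest on assumed feature counts, prevalences, effect sizes and FDR levels. More extreme assumptions (95% of features at 3% prevalence, with features absent from all patients also counted) gave up to 29 points. A reader might take a loss of 15–22 points as a property of this plan. It is not: that size appears only where rare features dominate and the marker is strong. The analysis is exploratory, and neither the primary response-rate test nor the stage 1 decision is touched.

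**What to change.** In section 10.3, before any outcome-linked molecular analysis:

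1. State the FDR level q and define the family of features to which the correction applies.
2. Before applying Benjamini-Hochberg, drop each binary feature whose smallest attainable two-sided Fisher p-value exceeds q, given only the number of altered patients and the number of responders among those analysed.
3. Apply the correction to the remaining features and report how many were dropped.

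At q = 5% and 7–10 responders this means at least 3 altered patients. The minimum should be recomputed from the actual margins, for example if responders are fewer or the trial stops at 14 patients. The cost is a short addition to 10.3 and a small amount of code, with no extra data and no loss of error control.
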